4.4 Measurements recorded daily in a diary

A diary will be filled in at home during the entire study in the morning after taking the morning dose and at night after the evening before going to bed. The following variables will be recorded:

- i) Intake of study medication (if, time and if with food)
- ii) Occurrence of any adverse effects.
- iii) Intake of any incidental medication

The subjects will record the time (morning and evening) that the study medication has been taken. The recordings are a measurement of compliance.

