ENDPOINTS:	
EFFICACY
 
 1. Behavioral improvement with the validated scales for autistic spectrum disorders 2. Examination by child psychologist 
SAFETY
 
 1. Adverse events, especially frequency and intensity of agitation episodes 2. Modification of vital signs: blood pressure, heart rate, respiratory rate, body temperature. 3. Modification of laboratory tests: Haematology: RBC, MCHC, MCH, MCV, RDW, Hct, Hb, WBC Differential count –lymphocytes monocytes, neutrophils, eosinophils, basophils; CD45+; blood cultures Biochemistry: Serum - Bilirubin (total) AST, ALT, LDH, glucose, urea, creatinine, sodium, potassium, chloride, calcium., MB microbiology; IP – Inflammatory panel
SAMPLE SIZE:	at least 25 patients, optimum 40 patients enrolled
STATISTICAL ANALYSIS:	Summary statistics will describe the safety variables. Significance testing will be done using analysis of variance for continuous and chi-square test for categorical variables. ($\alpha = 0,05$)

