4 STUDY MEASUREMENTS AND ENDPOINTS

In this study the following endpoints will be measured/recorded

1. Efficacy - difference in the scores on the questionnaires M-CHAT, Q-CHAT and CAST before and after each treatment

2. Safety – type, severity, duration, treatment and amelioration of each of the adverse effects occurring during respective treatments.

4.1 Primary Safety Endpoints.

–

1. Adverse events (type and frequency)
2. Physical examination parameters (body mass, height, etc)
3. Vital signs: blood pressure, heart rate, respiratory rate, body temperature
4. Laboratory tests
 - HLA testing by genetic sequencing
 - Haematology: CBC - RBC, HB, MCHC, MCH, MCV, RDW, Hct, Hb, WBC Differential count –lymphocytes monocytes, neutrophils, eosinophils, basophils, flowcytometry - CD34+, TNC, viability %
 - Microbiology – presence and sensitivity of pathogens
 - LFTs Serum - Bilirubin (total and conjugated) AST, ALT, GGT, LDH, glucose
 - IP – serum protein electrophoresis, ESR, CRP, fibrinogen
 - Els - sodium, potassium, chloride, calcium, magnesium.

4.2 Measurements at each visit.

See section 3.1.1 for the visit schedule.

Visit 0: Screening Visit

Patients will be examined within 14 days prior to the first ingestion of the investigational products to assess their eligibility to participate. For each child both parents will consent in writing (Appendix 1, Informed Consent Form) to the screening process before the start of the examination. The consent form will also include the study information leaflet.

The examinations and investigations will include:

- Medical history, including history of past use of medications, demographics (date of birth, sex, race) and ASD diagnosis.
- Physical examination including assessment of general appearance, cardiovascular, lungs, mouth, throat and abdomen and measurement of height and body weight. The examination will be made in accordance with the normal clinical routines at the trial center.
- Vital signs: systolic and diastolic blood pressure in supine (after 5 minutes rest) and standing positions (1minute), pulse, respiratory rate and oral temperature.
- Laboratory tests: HLA, Haematology, (see section 4.4.3.2); baseline plasma levels of IP, Els, LFTs (these can be drawn also at V1 if considered by the study PI)

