4.3 Specific detail on measurements

4.4.1 Adverse events

An adverse event is the development of an undesirable medical condition - e.g. symptoms or abnormal results of an investigation - or the deterioration of a pre-existing medical condition (not relevant in this study). AE's will be collected by means of a standard question: "Have you had any health problems since the previous visit?" AE's will be recorded at every visit. Spontaneously reported AE's and/or observed AE's and the subject's response to this question will be recorded on the AE form with information about seriousness, action taken, date of onset and recovery, maximum intensity and outcome. The subjects will be asked to assess the intensity of the reported Adverse Event according to the following scale:

Mild = awareness of sign or symptom, but easily tolerated
Moderate = discomfort sufficient to cause interference with normal activities
Severe = incapacitating, with inability to perform normal activities.

A Serious Adverse Event is an adverse event occurring during any phase of the study and at any dose of the investigational product or placebo, which fulfils one or more of the following criteria:

- Results in death;
- Is immediately life-threatening;
- Requires in-subject hospitalization;
- Results in persistent or significant disability or incapacity.

The causality of Serious Adverse Events (i.e. the relationship to study treatment) will be assessed by the investigators, who in completing the relevant Case Report Form must answer ‘yes’ or ‘no’ to the question “Do you consider that there is a reasonable possibility that the event may have been caused by the study medication?” The following factors should be considered when deciding if there is a “reasonable possibility” that an Adverse Event may have been caused by the investigational product.

- Time course of events and exposure to suspect drug – did the AE occur in a reasonable temporal relationship to the administration of suspect drug?
- Dechallenge experience – did the AE resolve or improve on stopping or reducing the dose of the suspect drug?
- Rechallenge experience - did the AE reoccur if the suspected drug was reintroduced after having stopped?
- Laboratory tests – has a specific laboratory investigation confirm the relationship?
- No alternative cause - the AE cannot be reasonably explained by another aetiology such as an underlying disease (not previously present), other drugs or environmental factors.

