There would not be a “reasonable possibility” of causality if none of the above criteria apply or where there is evidence of exposure and a reasonable time course, but any dechallenge is negative or there is another more likely cause of the AE.

In this study the Adverse Events will be noted from the interview at the time of visit and from the daily input in the diary.

4.4.2 12- Lead ECG

Standard 12-lead ECGs will be performed at the indication of the anesthesiology doctor if necessary.

The Bioclinica Laboratory will perform all the clinical laboratory investigations.

The samples will be processed and shipped as per instructions of the pathology laboratory.

For all laboratory investigations the investigator will receive actual printouts of the data from the Laboratory. A signed original printout will be attached to the CRF and a copy thereof will be filed in the subject file. The reference ranges will be provided in the clinical trial manual (investigator’s file) together with the descriptions of the laboratory methods used. The laboratory will provide normal ranges on each report to ease the investigator’s assessment.

As part of the overall safety monitoring plan, the safety monitor ([name]) will also assess the data, particularly those falling outside the normal range.

The blood samples will always be taken before the first trial medication dose for that day is taken. The blood samples will be collected in tubes labeled with the following information: patient name; test type (HLA, biochemistry, hematology, flowcytometry); blood sample number (visit 2, 3,4 or 5) and sampling time.

Blood samples will be handled according to the protocols for testing of the respective laboratories

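### The home diary asks about adverse effects and times its morning entry to a dose that only treatment B has, so adverse event capture can differ between treatment B and cord blood

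*Combined protocol and SAP*

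**What the plan says.** Two terms are used for safety.

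- **Events.** The synopsis endpoint is "Adverse events, especially frequency and intensity of agitation episodes". Section 4.1 lists "Adverse events (type and frequency") first. Section 4.4.1 defines an adverse event with no reference to cause and elicits it at every visit with "Have you had any health problems since the previous visit"? Section 5.2 lists adverse events per treatment group.
- **Effects.** Item 2 of Section 4 sets the safety endpoint as "type, severity, duration, treatment and amelioration of each of the adverse effects occurring during respective treatments". Diary item ii in Section 4.4 is "Occurrence of any adverse effects".

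The diary supplies adverse event data: Section 4.4.1 says that events are "noted from the interview at the time of visit and from the daily input in the diary". On timing, Section 4.4 says "A diary will be filled in at home during the entire study in the morning after taking the morning dose and at night"; the night entry is made before bed.

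The study is open-label (Section 3.3.2), and parents report the events (synopsis). Section 4.4.1 describes investigator assessment of causality only for serious events. Treatment B is taken daily for 6 weeks and followed by 2 weeks without treatment (Section 3.1.1). Cord blood is a single infusion (synopsis).

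**The concern.** An adverse event is recorded whatever its cause. An adverse effect, read literally, is something the reporter already attributes to a treatment. If the diary prompts for the second and the analysis counts the first, a judgement about cause can enter the data at home. The person making it would be a parent who knows the treatment. For non-serious events the plan describes no later causality step that would show this had happened.

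The prompt is also uneven. During treatment B each morning brings a dose and, with it, a diary entry. After the infusion and in washout there is no dose to trigger the morning entry, although the diary is meant to continue.

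What is at stake is the secondary objective in Section 2, which asks whether the safety profiles of the two treatments differ. Agitation is the sharpest case. The synopsis singles it out, and Section 1.2 (Study Rationale) treats agitation as part of the presenting picture in some children. Whether a given bout counts as an effect or as the child's usual behaviour is therefore a real question for a parent.

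**Working it through.** The documents state no capture rate, so there is no plan figure to reproduce. The check is a comparison of the text, followed by an illustration on assumed values.

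**Text.**

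1. *Term.* The synopsis, Section 4.1, Section 4.4.1 and Section 5.2 say events. Section 4 item 2 and diary item ii say effects. Section 4.4.1 makes the diary a source of events, so the prompt and the endpoint do not match.
2. *Timing.* V5 is 52 weeks after V1. Daily dosing takes up 6 of those weeks, so the morning anchor is absent in 52 − 6 = 46 weeks. Within the two 8-week treatment periods it is present in 6 of 8 weeks on B and 0 of 8 on cord blood.
3. *Recall at visits.* V1 to V2 and V2 to V3 are 8 weeks each, so the visit question covers 8 weeks under either treatment.
4. *Counts.* The diary asks for occurrence and not for number of episodes, while the synopsis and Section 4.1 both want frequency.

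**Illustration (all inputs assumed).** Let the true event rate be r under both treatments. Let the visit capture a fraction s of events, and the diary a fraction d_B on B and d_A on cord blood. Suppose the two sources act independently.

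- Observed rate = r × [1 − (1 − s)(1 − d)]
- Spurious gap (B minus cord blood) = r × (1 − s) × (d_B − d_A)

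With r = 40%, d_B = 80% and d_A = 40%:

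| Visit capture s | Observed on B | Observed on cord blood | Gap |
|---|---|---|---|
| 30% | 0.4 × (1 − 0.7 × 0.2) = 34.4% | 0.4 × (1 − 0.7 × 0.6) = 23.2% | 11.2 points |
| 50% | 0.4 × (1 − 0.5 × 0.2) = 36.0% | 0.4 × (1 − 0.5 × 0.6) = 28.0% | 8.0 points |
| 90% | 0.4 × (1 − 0.1 × 0.2) = 39.2% | 0.4 × (1 − 0.1 × 0.6) = 37.6% | 1.6 points |

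**Range.** Keep d_B at 80% and let r run from 20% to 60%, s from 30% to 90%, and d_A be 40% or 0.

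- Smallest gap: 0.2 × 0.1 × 0.4 = 0.8 points.
- Largest gap: 0.6 × 0.7 × 0.8 = 33.6 points. This needs a diary that records nothing after cord blood, which is an extreme assumption.

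If d_A = d_B the gap is 0. If parents record more after the infusion than during B, the sign reverses.

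**The case against.** The strongest reply is that one loosely chosen noun is being made to carry too much. Section 4.4.1 treats diary entries as adverse events under its own neutral definition, so *effects* may simply be a synonym. Other routes also catch events whatever their cause:

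- the neutral visit question, with spontaneously reported and observed events also recorded at each visit;
- examination, vital signs and laboratory tests at V2 (Section 4.2), with abnormal investigation results counted as events by the Section 4.4.1 definition;
- diary item iii, which asks about incidental medication.

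The diary is kept throughout, and its bedtime entry, as written, is not expressly tied to a dose. A twice-daily diary also gives at least a count of entries with a problem.

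Most of this stands, and it rules out several stronger readings.

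- A reader might infer that parents do filter events by presumed cause. No section tells them to. The wording permits it but does not establish it.
- A reader might infer that the visit question is the only neutral source, so that anything missing from the diary is lost. The routes above show otherwise.
- A reader might infer that the bias must inflate treatment B. Unblinded parents could equally be more watchful after an invasive infusion.
- A reader might go on to a false-positive rate for a paired test. That would rest on assumed capture rates and on a test that the plan does not name. Section 5.2 lists events individually, and the synopsis gives summary statistics for safety and chi-square for categorical variables.

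The reply does not remove the mismatch between diary prompt and endpoint. Nor does it supply a morning entry time for days without a dose, or a count of episodes within an entry.

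**Conclusion.** The inconsistency is real, and it lies in a source that the protocol uses for its adverse event data. It leaves room for diary capture to differ between daily treatment B and a single infusion, which bears on the secondary safety comparison. The size and direction cannot be determined from the documents. The illustrative 1.6 to 11.2 points assume a 40% true rate on both treatments, 80% against 40% diary capture and independent sources. How much of any gap survives depends mainly on how complete the visit interview is. This is a problem of wording and ascertainment in one of several sources, not a numerical error, and it does not touch the efficacy objective. It is a cheap improvement, best made before data collection because it changes what is written down at home.

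**What to change.** 1. In Section 4 item 2, use *adverse events*, to match Sections 4.1, 4.4.1 and 5.2.
2. Reword diary item ii to ask for *any new or worse health problem, whether or not you think a treatment caused it*, with the number of episodes.
3. Replace the dose-linked morning entry with fixed morning and bedtime entries on every diary day, in the cord blood, treatment B and washout periods alike. Keep medication intake as a separate item.
4. In Section 5.2, state that events are taken from the diary and the visit interview by the same rule for both treatments, with the source of each event flagged. The report can then show whether the diary contributes differently under the two treatments.

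The cost is a few lines of text and a revised diary page. The downside is that more unrelated childhood complaints will be recorded, so raw event rates will look higher under both treatments. The change does not remove reporting bias that comes from open-label treatment itself.

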5 STATISTICAL METHODS

5.1 Determination of sample size

Based on literature we expect that a sample size of minimum 25 participants will be needed in order to observe an alpha value of 0.05 (95% probability) with a p value of 0.05 and a power of 80%. ANOVA testing will be performed on the respective groups of patients

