Final Protocol:	June 2019	Clean File:	June 2019
Ethics Approval:	January 2019	Statistical analysis:	
Clinical Phase:		Study Report:	
OBJECTIVES:	To compare the safety and efficacy of administering intravenous autologous cord blood versus personalized noninvasive treatments to children with developmental disorders of the autistic spectrum		
STUDY DESIGN:	An open-label, pilot crossover study over a 12-month period. Participants will be screened and randomized at Visit 0 and at visit V1 will be receiving either intravenous umbilical cord blood or noninvasive treatment. At V2, at 2 months after V1, the other treatment is administered and subsequently the child will be evaluated by questionnaires and child therapist. Parents will report adverse events and complete the M-CHAT, Q-CHAT and CAST questionnaires. Modifications on these questionnaires will be analyzed statistically as a quantitative measure of child's improvement.		
SUBJECTS:	
Inclusion criteria Males and females between 3 and 7 years of age:
 
 • parents informed of the nature of the study and will give written informed consent, • have body weights between 10-30 kg, • have no clinically significant abnormal values on hemoleucogram during screening, • be on no regular medical treatment • have no known allergies to treatments 
Exclusion criteria
 
 • Any genetic or metabolic disease or condition which might compromise the haematopoietic, renal, endocrine, pulmonary, central nervous, cardiovascular, immunological, dermatological, gastrointestinal or any other body system. • History of allergic conditions – asthma, urticaria, eczema. • History of autoimmune disorders 		

	
 • Intake of any medication within 14 days before start of the study • Presence of significant abnormal hemoleucogram results during screening.
TREATMENT TO BE EVALUATED	
Active Treatment A: Autologous umbilical cord blood administered intravenously as single treatment .
 
Active Treatment B: Personalized daily treatment following evaluation with a combination of intranasal Oxytocin; Curcumin; Lecithin, Piracetam, Tecfidera; PQQ; Magnesium citrate and vitamin B6

DURATION OF STUDY	12 months

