2 STUDY OBJECTIVES

The primary objective of this study is to investigate the comparative efficacy of the UCB infusion and the non-invasive treatments for improving the functioning of children with ASD.

A secondary objective is to determine whether there are significant differences in the safety profiles of the two treatments administered

In addition there will be an evaluation of the structural changes in the CNS of the children with ASD, done by MRI

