3 STUDY PLAN AND PROCEDURES

3.1 Study design

This is a twelve months long, open-label, crossover study to evaluate the comparative efficacy and safety of UCB versus non-invasive treatments in children with ASD. Each participant will receive both treatments in a random sequence.

The UCB is autologous, previously harvested at the child's birth and cryopreserved in liquid nitrogen for later use.

The UCB infusion was performed at Angiomedica Hospital, [name] as main site and in two additional clinical sites: Medicover Hospital, [name], and Ponderas Academic Hospital, [name], all in Bucharest, Romania by anesthesiologist and pediatric physician, based on the Duke protocol.

Prior to UCB infusion, HLA typing of the child will be performed at the National Institute of Hematology, as well as the HLA typing of the UCB prior to thawing – for positive identification. During this time the UCB collection will be kept in liquid nitrogen for a maximum of 72 hours, after which thawing and preparing of the UCB for infusion will be performed by [name]; the thawing is done in optimal conditions for preserving simultaneously both sterility and viability of the cryogenated cells - the Vita 34 or Rubinstein protocols; testing for viability will be done with Trypan Blue and flowcytometry. Choosing optimal conditions is based upon the minimum number of processing steps necessary (fewest number of centrifugations and shortest time of processing, with best recovery of various stem cells) and ensuring sterility.

The non-invasive treatment combination is prescribed by the study investigator after the three questionnaires are answered and an evaluation by child therapist/psychologist is performed independently. This treatment is

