3.3.2 Randomisation

Because it is an open-label study, there is no need for blinding/assigning participant numbers. Each participant will be randomly assigned to begin the study either with the UCB infusion or the non-invasive treatment.

Eligible patients, who for whatever reason, do not report to the clinic to receive the first treatment after having been selected for the study will be referred to as discontinuers in the report. A patient who, for whatever reason, withdraws or is withdrawn from the study after having been enrolled, will be classified as a dropout, and identified as such in the relevant Case Report Form (CRF).

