5.2 Statistical analysis

A single statistical analysis will be performed at the end of the study. An intention to treat (ITT) approach will followed, i.e. statistical analysis of safety will be based on data from all patients and from whom meaningful data were collected. Data will be displayed graphically for visual inspection. Descriptive statistics will be presented as means, SEM and ninety percent confidence levels of the means.

Baseline characteristics. The subject disposition will be summarized. Protocol violations will be listed per subject, describing the nature of the violation. Subjects failing to complete the study (as well as the times and reasons for discontinuation) will be displayed. The demographic, background and baseline data will be presented descriptively.

Analysis of Safety. Adverse Events, as reported throughout the course of the trial will be listed individually, per treatment group. Pre-, study and post-study findings of **physical examination, vital sign variables, laboratory variables** (haematology, clinical chemistry and urinalysis), and 12-lead ECG if needed will be listed individually and summarized; values outside the normal range will be listed.

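### The crossover has no specified efficacy analysis: the named ANOVA fixes no child or period term, and the two-period comparison rests on an unexplained 8-week limit on treatment effect

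*Combined protocol and SAP*

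**What the plan says.** The Synopsis describes "An open-label, pilot crossover study over a 12-month period". Section 2 states that "The primary objective of this study is to investigate the comparative efficacy of the UCB infusion and the non-invasive treatments". Section 3.1 says "Each participant will receive both treatments in a random sequence", and Section 3.3.2 confirms random assignment of the first treatment. Section 4 defines efficacy as the "difference in the scores on the questionnaires M-CHAT, Q-CHAT and CAST before and after each treatment".

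On testing there are two sentences. Section 5.1: "ANOVA testing will be performed on the respective groups of patients". Synopsis: "Significance testing will be done using analysis of variance for continuous and chi-square test for categorical variables", at alpha 0.05. Section 5.2 covers descriptive statistics, baseline data and safety. It has no efficacy model, and it explains intention to treat only in terms of safety: "statistical analysis of safety will be based on data from all patients and from whom meaningful data were collected".

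Section 3.3.1 takes each treatment to be active for no longer than 8 weeks and gives no reason. Section 1.2 (Study Rationale) describes UCB as given once. Section 3.1.1 puts the switch at V2 (week 8) and later questionnaires at weeks 16 (V3), 24 (V4) and 52 (V5). In children who start with the noninvasive treatment (B), V2 falls two weeks after B stops.

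**The concern.** A two-treatment, two-period crossover yields two results per child, and these are not independent. A valid analysis compares a within-child contrast between the two randomised sequences, which removes both the child and the period effect. The plan names no child, period or sequence term and does not say whether the groups are the two sequences or the two treatments. It also ranks none of its three questionnaires.

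The primary objective is comparative and the study is open-label, so this choice should be fixed before the data are seen. Otherwise the false-positive rate of the main comparison is set by a later decision. The 8-week limit matters for a second reason: every two-period estimate depends on what happens to the first treatment's effect between V2 and V3.

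**Working it through.** **The plan's own figure.** Section 5.1 gives 25 participants for alpha 0.05 and 80% power. This cannot be reproduced, because no effect size, SD, correlation or sidedness is given. Back-solving at two-sided 0.05:
- paired, normal approximation: (1.960 + 0.842)/√25 = 0.56 SD of the within-child difference;
- crossover with period, t with 23 df: 0.585 of the same SD;
- 13 v 12 compared as parallel groups: 1.17 SD of the outcome compared.

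The sample size therefore does not reveal which analysis was meant.

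**Assumed inputs (none are in the plan).** Score SD 1; visits V0, V2, V3; visit correlation r from 0.5 to 0.8; 12 v 13 children; no treatment effect.

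**Two changes treated as independent groups.** The changes are V2−V0 and V3−V2, and V2 enters them with opposite signs. If their correlation is c, the false-positive rate is about 2[1 − Φ(1.96/√(1−c))].
- Equal correlation: Var(change) = 2(1−r), Cov = −(1−r), so c = −0.5 for every r. 1.96/√1.5 = 1.60, which gives 11.0%. Simulation (60,000 trials): 10.8-10.9%.
- AR(1): Cov = −(1−r)², so c = −(1−r)/2. At r = 0.5, c = −0.25, which gives 8.0%; at r = 0.8, c = −0.10, which gives about 6.2%. Simulation: 7.9% and 6.2%.
- Child-specific linear trend with variance k times the visit error variance: c = (k−1)/(k+2). Simulation: 10.9%, 5.0%, 2.5% and 0.7% at k = 0, 1, 2 and 4.

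In the same setting, first-period change compared between sequences, first-period ANCOVA and the change-score crossover between sequences all give 4.8-5.2%.

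**Carryover.** Let a and b be the UCB and B effects at V2, and L and M the fraction by which each changes by V3. Then:
- UCB-first: V2 = a, V3 = a(1+L) + b.
- B-first: V2 = b, V3 = a + b(1+M).

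Half the difference between sequences estimates:
- V2−V3: [(a−b) − aL + bM]/2;
- (V2−V0)−(V3−V2): (a−b) − aL/2 + bM/2.

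| Between V2 and V3 | V2−V3 | (V2−V0)−(V3−V2) | First period |
|---|---|---|---|
| Both gone (L=M=−1, the Section 3.3.1 premise) | a−b | 1.5(a−b) | a−b |
| Both persist in full (L=M=0) | (a−b)/2 | a−b | a−b |
| UCB persists, B gone (L=0, M=−1) | a/2 − b | a − 1.5b | a−b |

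With a = 0.8 and b = 0.3 (true difference 0.50), the V2−V3 contrast gives 0.50, 0.25 and 0.10 in the three rows, and the change contrast gives 0.75, 0.50 and 0.35.

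In the third row with a = b there is no true difference, yet both contrasts centre on −a/2. The change contrast then rejects in 13-16% of trials at effects of 0.37-0.59 SD, and in 30-45% at 0.72-1.04 SD. The V2−V3 contrast has the smaller variance, so it rejects more often: at r = 0.5 with 0.5 SD of UCB carryover into V3, 22.1% against 10.9%. The first-period comparison stays near 5%.

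**Precision at 80% power** (0.585 × SD of the within-child contrast).
- V2−V3: 0.585 × √(2(1−r)) = 0.59 to 0.37 SD.
- Change contrast, equal correlation: 0.585 × √(6(1−r)) = 1.01 to 0.64 SD.
- Change contrast, AR(1): 0.585 × √(2(1−r)(3−r)) = 0.93 to 0.55 SD.
- First-period ANCOVA: 1.04 to 0.72 SD.

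**The case against.** The best defence is that the sentence can be read benignly. Groups of patients most naturally means the two randomised sequences, and comparing their first-period change is valid. ANOVA also includes repeated-measures ANOVA. The 11% figure needs 25 children to be analysed as 50 independent records, and AR(1) correlation lowers it to 6-8%. All of this stands. A reader might infer that the plan's test has an 11% error rate; the documents do not support that, because they commit to no reading and give no covariances.

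A reader might also infer that the plan leaves open whether change or raw post-treatment score is tested. It does not: Section 4 defines change, and the Synopsis likewise speaks of modifications on the questionnaires. What is open is the model, the baseline for the second change and the primary scale.

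On carryover, a reader might take visits to week 52 as evidence that UCB lasts beyond 8 weeks. They are not; the documents neither show nor exclude persistence. The rationale also asks whether other substances can add to UCB, so some overlap is deliberate. If the effects do overlap, however, V3 in UCB-first children is not a result for B alone.

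Finally, pilot status is a fair plea for modest ambition, but the plan still commits to significance testing at 0.05 and claims 80% power.

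**Conclusion.** The concern holds in this form: the primary comparison of the crossover has no determinable analysis, and the choice is not cosmetic. Under the assumed correlations at 12 v 13, one available reading gives about 11% or 6-8% false positives at a nominal 5%, falling below 5% when children's trends differ widely. A between-sequence comparison gives about 5%. These figures show dependence on the reading and do not estimate this trial's error rate.

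The unexplained 8-week limit is a separate weakness that a period-adjusted model does not cure. No two-period contrast is safe by default. Under the plan's own premise V2−V3 is unbiased, while the change contrast overstates the difference by 50%. If both effects persist in full, the change contrast is unbiased and V2−V3 is halved. If UCB persists and B fades, both are biased. Only the first-period comparison is free of carryover.

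**What to change.** Replace the Section 5.1 sentence, and add an efficacy paragraph to Section 5.2, as follows.

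1. Name one primary questionnaire in advance.
2. Specify a within-child, period-adjusted comparison between the two randomised sequences. Under the Section 3.3.1 premise, use change from V0 at V2 and at V3, so that the contrast is V2 minus V3. State that V0 is the baseline for both changes.
3. If (V2−V0)−(V3−V2) is preferred, state that it tests a = b at 5% under equal washout, overstates the difference by 50% when both first-treatment effects are gone by V3, and is unbiased when both persist in full.
4. Always report beside it the first-period comparison by randomised first treatment (ANCOVA of V2 on V0) as the carryover-free estimate, with no switch based on a carryover test.
5. State that the two-period result relies on the 8-week assumption. Where the two results disagree, claim no difference from the two-period result alone.

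The cost is analysis wording only, with no added patients or visits. Three downsides should be stated. The first-period estimate is imprecise (80% power only for about 0.7-1.0 SD at 12 v 13). In B-first children it measures B two weeks after it stops. The V2−V3 contrast is more exposed than the change contrast if UCB persists.
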